### I. *Target Population and Inclusion/Exclusion Criteria*

A final sample of 42 smokers with AUD (balanced by sex) will be recruited from the community.

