#### Exclusion Criteria

- a) Recent (30 day) illicit drug use (with the exception of cannabis) based on self-report or toxicology screen
- b) Meeting DSM-5 criteria for a past-year substance use disorder other than alcohol use disorder, tobacco use disorder, or mild cannabis use disorder
- c) Significant alcohol withdrawal, based on a Clinical Institute Withdrawal Assessment for Alcohol-revised (CIWA-Ar) score of 8+ at baseline medical visit, or any reported history of severe withdrawal symptoms (e.g., seizures, DTs).
- d) Past 30-day use of nicotine replacement
- e) Past 30-day use of SSRIs, other psychiatric medications, or weight control medications
- f) Lifetime diagnosis of severe mental illness (e.g., psychotic or bipolar I disorder)
- g) Significant medical or neurological illness based on medical staff (i.e., physician or nurse practitioner) evaluation including severe hepatic impairment or cirrhosis, insulin dependent diabetes
- h) Current alcohol or smoking cessation treatment or efforts to cut down on drinking/smoking
- i) Medications which are contraindicated for use with lorcaserin (e.g., bromocriptine, cabergoline, dapoxetine, dihydroergotamine, ergoloid mesylates, ergonovine, ergotamine, methylene blue, methylergonovine, nicergoline, pergolide, thiorizadine) or which have a

significant interaction with lorcaserin (e.g., bupropion, doxorubicin, eliglustat, linezolid, perhexiline, rasagiline, safinamide, selegiline, tamoxifen) 

j) Body mass index (BMI) under normal range (<18kg/m^2) 

k) History of significant cardiovascular conditions including history of arrhythmias or heart block, heart failure, valvular heart disease, heart attack, stroke, unstable angina

l) Abnormal electrocardiogram (ECG) results

m) Currently nursing, pregnant, or anticipating pregnancy

n) *history of suicide attempt or recent suicidal ideation (i.e., Suicidal thoughts (intent or plan) in the last month)*

*o) Plans to travel outside of the Albuquerque area during the study period, or inability to commit to entire duration of study (6 weeks of potential availability)*

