## II. *Participant Enrollment*

We anticipate phone screening up to 1000 individuals and may enroll up to 100 participants in order to obtain a final sample of 42 eligible participants who complete all study visits.

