## V. *Data Collection Procedures*

In total, participation in this study will take roughly 20-25 hours over a period of approximately 5 weeks. This includes a screening visit (up to 3 hours), a baseline visit (up to 3 hours), a medication refill visit (1 hour), and two follow-up laboratory visits (6-8 hours each). Participants will receive calls twice from staff during each of the medication phases to check in on side effects (<15 minutes per call).

Participants will be asked to complete the following procedures:

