### Screening and Baseline Data Collection Visits

The in-person screening visit will include both a clinically-oriented screen by a medical staff member, and self-report and interview questions, conducted by the research assistant or medical staff member. The staff will administer a breathalyzer and urine drug screen (for females, the test will include a pregnancy screen), and then briefly review and verify information collected over the phone. Participants who have a BAC greater than 0.00 will be rescheduled and given snacks and water until their BAC is reduced to a safe level (BAC<.02-.04g%), in accordance with NIAAA guidelines (or to 0.00 in the event that the participant drove to the session). If participants are unable to arrange for transportation, we will provide a taxi or car ride (e.g., Uber) voucher for up to \$25 per ride. In addition to BAC, we will measure potential alcohol withdrawal symptoms (CIWA) expired alveolar carbon monoxide (CO).

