Additional screening criteria, including symptoms of alcohol and nicotine dependence, and aspects of medical history (see criteria listed above) will be assessed. The **Structured Clinical Interview for DSM-V**  will be used to assess inclusionary/exclusionary diagnoses. The **Timeline Follow-Back (TLFB)**  will be used to assess alcohol, cigarette and other drug use in the 90 days prior to baseline and during the experimental phase. The urine sample will be used to test for the presence of several drugs (for example, marijuana, heroin, cocaine, methamphetamines, opiates). If a participant tests positive for drugs other than marijuana (or if females screen positive for pregnancy) the participant will be excluded from the study. Additionally, participants will complete a blood draw (up to 20 ml) for a complete blood count (CBC), a basic metabolic panel, baseline measure of nicotine metabolites, a hepatic function panel. The baseline blood sample will also serve as the sample for DNA analysis. Participants will also complete an ECG test. Blood draws will be performed by trained research staff. ECG results will be evaluated by qualified medical staff. During the medical history any medications that the participant is taking will be checked for interactions with lorcaserin in an established online database such as Epocrates or Lexicomp, and prescribing medical staff will be contacted for dose adjustments, if deemed necessary. Any incidental medical findings during the assessment or subsequent participation in the study will be communicated by the MD or NP directly to the participant. If indicated, the participant will be instructed to follow-up with their GP, or will be provided with a referral.

If a participant shows symptoms of acute alcohol withdrawal (e.g., based on the CIWA cutoff noted above), the study medical staff will take appropriate steps to manage the symptoms (including escorting the participant to UNM Hospital if necessary). Participants who meet all study eligibility procedures will be provided with a study overview, and informed consent, locator, and collateral contact information will be obtained.

If results of the baseline screening/medical assessment indicate that the participant is eligible, they will be scheduled for a return baseline visit. This visit will include a more comprehensive orientation to the study, a questionnaire battery, cognitive tasks, and dispensing of the first set of study pills.

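### No pregnancy test is scheduled at either pill-dispensing visit, and at the follow-up visits the observed pill comes before the urine test

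*Combined protocol and SAP*

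**What the plan says.** Exclusion criterion (m) bars anyone "Currently nursing, pregnant, or anticipating pregnancy". At in-person screening a urine sample is taken and, "for females, the test will include a pregnancy screen"; a positive result excludes the participant (Screening and Baseline Data Collection Visits). Table 1 has a matching row under Screening, and a combined urine test for pregnancy, drugs and riboflavin under each of follow-up visits 1 and 2.

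Pills are handed out at two other visits. The first is the baseline visit, a return appointment made once eligibility is confirmed. Beyond orientation, its content is given as "a questionnaire battery, cognitive tasks, and dispensing of the first set of study pills". Neither that text nor the Baseline/First Dispensing rows of Table 1 include a urine or pregnancy test. The second is "a medication refill visit (1 hour" allotted), whose Table 1 entries under Washout are the drinking calendar, dispensing and an appetite questionnaire.

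At each follow-up visit the participant takes the morning pill under observation soon after arrival. A smoking break, snack and assessments follow, then the medical assessment with its urine screen, then the alcohol procedure. The text makes the alcohol procedure conditional on there being no medical contraindication; it does not make the pill conditional.

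**The concern.** A test at the end of a course cannot enforce an exclusion meant to prevent exposure during that course. Each course is preceded by some earlier test, so the gap is confined to pregnancies that first become detectable in one of two intervals: between screening and baseline, or during the nominal 7-day washout. For those women the scheduled result arrives after the home doses and after one more pill given by staff.

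No maximum interval from screening to first dispensing is stated. The supplied text has no contraception requirement either, so protection in these intervals rests on stated intention under criterion (m) and on self-report. What is at stake is participant safety under the plan's own rule; the primary analysis, power and alpha are untouched.

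**Working it through.** The plan gives no figure of its own to reproduce. The check sets the visit text beside Table 1 and then counts days, doses and tests.

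**Where tests and pills fall**

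| Visit | Pregnancy test listed | Pills |
|---|---|---|
| Screening | Yes (text and Table 1) | None |
| Baseline | No (text or Table 1) | First 7-day supply |
| Follow-up 1 (Day 7) | Yes (Table 1), before the priming drink | Observed pill, listed before the urine test |
| Washout / second dispensing | No (Table 1) | Second supply |
| Follow-up 2 (Day 7) | Yes (Table 1), before the priming drink | Observed pill, listed before the urine test |

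That is 3 scheduled tests, with none at the 2 dispensing visits.

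**Age of the last test at dispensing**
- First dispensing to follow-up 2: 7 (course) + 7 (washout) + 7 (course) = 21 days.
- Section V states "In total, participation in this study will take roughly 20-25 hours over a period of approximately 5 weeks". 5 × 7 = 35, and 35 − 21 = 14 days at most are left between screening and baseline.
- Criterion (o) asks for "6 weeks of potential availability". 6 × 7 = 42, and 42 − 21 = 21 days.
- Assumed range for the first supply: 0 to about 14 days (up to about 21) from test to dispensing. The next test is 7 days after dispensing, so 7 to about 21 (up to about 28) days separate the two tests. The upper values give all the slack to this one interval.
- Second supply: the last test is a nominal 7 days old at dispensing, and 7 + 7 = 14 days separate the two tests. The plan allows slight deviations from these intervals.

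**Doses taken before the result**
- At 10 mg twice daily, a supply is 2 × 7 = 14 tablets, more if extra days are given.
- Doses up to and including the observed Day 7 morning pill depend on when dosing starts, which is an assumption:
  - Evening of Day 1: 1 + (5 × 2) + 1 = 12.
  - Morning of Day 1: (6 × 2) + 1 = 13.
  - Evening before Day 1: 1 + (6 × 2) + 1 = 14.
- Home doses are therefore 11 to 13, plus the one given on site.

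**Women and added tests, assuming half of participants are women**

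The sections differ on what 42 means. Target Population says "A final sample of 42 smokers with AUD (balanced by sex) will be recruited from the community"; Participant Enrollment says the trial "may enroll up to 100 participants in order to obtain a final sample of 42 eligible participants who complete all study visits"; Statistical Power randomises 42, allowing for roughly 20% attrition.
- 42 randomised: 42 / 2 = 21 women; × 2 dispensings = 42 tests; × 5 min = 210 min = 3.5 h.
- 42 completers at 20% attrition: 42 / 0.80 = 52.5, so 53 randomised, about 27 women; × 2 = 54 tests; × 5 = 270 min = 4.5 h.
- Extreme case, all 100 enrolled receive both supplies: 50 women; × 2 = 100 tests; × 5 = 500 min, about 8.3 h.

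These are upper values. Ages run to 65, so not all women are of childbearing potential, and dropouts would not reach the second dispensing.

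**Room in the visits**
- Baseline rows in Table 1 sum to 119 min; 119 + 5 = 124 of the 180 allowed.
- Second-dispensing rows: 10 + 10 + 2 = 22 min; 22 + 5 = 27 of the 60 allowed.

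**The case against.** The strongest reply is that Table 1 is not exhaustive. It has no row for follow-up heart rate and blood pressure, the Day 7 pill count, the nicotine withdrawal scale at baseline, orientation or the first dispensing itself. The refill visit is allotted an hour but its rows fill 22 minutes. A missing row is therefore weaker evidence than it looks, and the spare minutes may not all be spare. This carries some weight, most of all for the second dispensing, where the text adds little to the table. It does not remove the point. The baseline text omits the test as well as the table, and the plan lists pregnancy testing explicitly at the other three visits.

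Second, the data and safety monitoring plan and the prescribing information are attachments that were not supplied, and the consent pages were removed. Any of them could require contraception or a test before dispensing. That cannot be checked. If they do, Table 1 should still show it.

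Third, the gap is narrow and other safeguards exist. Women anticipating pregnancy are excluded, a medical history and physical examination are taken, and staff call on about days 2 and 4. There is also a daily survey of side effects and a medical contact number. One course is placebo, and the retest precedes the alcohol. All of this is true and limits the size of the problem. None of the self-report routes is described as asking about pregnancy.

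Fourth, the documents state no fetal risk or pregnancy rate, so severity cannot be put as a number. That is accepted. The case rests on the plan's own exclusion and the low cost of applying it at the right time.

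**Conclusion.** The point holds. Followed as written, the plan gives pills to women whose last pregnancy test is of unstated age at the first dispensing (assumed 0 to about 14 days, at most about 21) and nominally 7 days old at the second. For a pregnancy that first becomes detectable in either interval, the scheduled result comes after about 12 to 14 doses, the last of them given on site just before the test.

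This rests on the supplied text and Table 1, on the nominal 7-day intervals, and on the unseen attachments not adding a test. No expected number of affected participants can be given. The change should be made because it is a cheap safeguard for an exclusion the plan already sets. Confidence is medium, mainly because of the unseen attachments.

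**What to change.** 1. At follow-up visits 1 and 2, collect and read the urine pregnancy test already scheduled there before the observed morning pill, and give the pill only if it is negative. This adds no test. Because every pill contains riboflavin, it also keeps that morning's dose out of the adherence sample.
2. Add the same urine test to the Baseline/First Dispensing and second-dispensing rows of Table 1 for women of childbearing potential, and dispense only after a negative result.

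The scheduled total rises from 3 tests to 5 per woman of childbearing potential, and the age of the last test at dispensing falls to 0 days at both visits. The cost is up to two 5-minute tests per woman at visits that already take place: about 3.5 staff hours over the trial if 42 are randomised, 4.5 if 42 must complete, and 8.3 in the extreme case. No new visit or staff is needed. Very recent conceptions, and those during a course, would still be missed.

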Participants will complete the following questionnaires, which will be programmed in RedCap software. A **Demographic Screening Questionnaire** will assess basic demographic factors (e.g., age, education, income). A **Locator** collects contact information for three to five individuals who can be contacted if a participant is unable to be reached by study staff for follow-up visits. Other baseline measures (to be administered by computer using RedCap software) will include the **Alcohol Use Disorders Identification Test** , **Self-Report of the Effects of Alcohol Questionnaire (SRE)** , **Fagerström Test of Nicotine Dependence** , and the **Nicotine Dependence Syndrome Scale** . Baseline measures that will be repeated at subsequent visit will include the **TLFB**, the **Penn Alcohol Craving Scale (PACS)** and **Tiffany Questionnaire of Smoking Urges (TQSU)** , the **Yale Craving Scale**, and the **Minnesota Nicotine Withdrawal Scale** . To assess potential medication effects on changes in motivation and self-efficacy for resisting alcohol/cigarettes, we will use alcohol and smoking **Contemplation Ladder** items, alcohol and cigarette **Abstinence Self-Efficacy (AASE and SEQ)** and **Inventory of Drinking Situations** scales . Given lorcaserin's effect on food intake, changes in appetite will be assessed with the **Three Factor Eating Questionnaire**  and the **Reward-Based Eating Drive Scale** . The **PROMIS** Depression scale and Beck Depression Inventory-II will be administered to assess potential depressive symptoms. If participants report suicidal ideation, standard MRN protocols will be followed, including further assessment of the participant by medical staff and/or the PI, offering a referral, and following up with the participant. The **Wechsler Test of Adult Reading (WTAR)** will be used to estimate intelligence. During the medication phases, side effects will be assessed with the **SAFTEE** questionnaire  and an **Adverse Events Checklist** .

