*Impulsivity/Learning Tasks:* To examine medication effects on behavioral measures of impulsivity and reward-based learning (as reported in preclinical studies), participants will complete computerized cognitive tests of impulsive action, attention, and reward-based learning at the baseline session, lasting roughly 45 minutes in total duration. These measures will be repeated at follow-up visits. Additionally, any measures noted above that would be expected to show change across sessions (or in response to medication) will be repeated at follow-up visits 1 and 2. These measures include: Stop Signal task, CPT, Reward Responsiveness Test, Monetary Choice Questionnaire, Food Discounting Task, Alcohol Purchase Task, and Cigarette Purchase Task.

The baseline session is projected to take approximately 2-3 hours. Patients will be given breaks, snacks, and bottled water as needed.

**Medication Schedule and Safety Monitoring.** Participants will receive the first 7-day supply of pills (medication or placebo, randomized and counterbalanced) at the completion of the baseline visit. In the first Phase II trial of lorcaserin for smoking cessation, the FDA-approved dose of 10mg BID (twice-daily) significantly increased abstinence relative to placebo, with a larger effect size relative to a comparison low-dose condition (10mg QD / once-daily) . The BID and QD conditions were equivalent on discontinuations due to adverse events (AE; 2.5% and 3.0%, respectively) . Therefore, we will use the FDA-approved dose of 10mg BID. Of note, steady-state plasma concentration occurs in 3 days. All pills will include a small amount of riboflavin to facilitate urinalysis as an index of adherence, and participants will be asked to bring their pill bottles at each visit. To monitor emergent side effects, the study staff will contact participants twice during the 7 day period (e.g., days 2 and 4). Participants will complete a brief web-based assessment each morning using Redcap (link texted by research staff or automated system), including 1) prior-day number drinks consumed; 2) number of cigarettes smoked; 3) side effects; and 4) medication

adherence for the prior day. Participants will be texted a link to the survey, which can be completed via smartphone. If preferred, participants can opt to receive an email link, or a text message with these questions embedded in a SMS text.

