**Table 1. Study Measures**

VISIT	MEASURE/PROCEDURE	TIME (MINS)
Screening	Consent	30
	Breath alcohol test	2
	Urine drug screen	5
	Urine pregnancy test (females)	5
	Expired CO	2
	TLFB	30
	SCID	60
	CIWA	5
	The Wechsler Test of Adult Reading (WTAR)	10
	Blood draw	5
Medical screen (may occur on different day than screening)	Physical Exam	10
	Medical History	15

VISIT	MEASURE/PROCEDURE	TIME (MINS)	
depending on availability)	EKG	20	
	CIWA	5	
Baseline/First Dispensing Visit	Demographics form	5	
	Locator form	10	
	CIWA	5	
	AUDIT	2	
	SRE	2	
	FTND	1	
	NDSS	3	
	TLFB	10	
	PACS	1	
	TQSU	1	
	Yale Craving Scale	5	
	Contemplation Ladder	1	
		Three Factor Eating Questionnaire	3
		Simplified Nutritional Appetite Questionnaire	2
		Reward Based Eating Drive Scale	2
		PROMIS Depression/BDI-II	4
		Stop signal	10
		CPT	10
		Reward Responsiveness Test	15
		Monetary Choice Questionnaire	2
		Alcohol Purchase Task	2
		Cigarette Self-efficacy (SEQ)	1
		Alcohol self-efficacy (AASE)	1
		Cigarette Purchase Task	2
		Inventory of Drinking Situations (IDS-30)	5
		Food delay discounting task	4
	SAFTEE	10	
Between Baseline & Follow up visit 1	Call participant on days 2 and 4 to assess side effects SAFTEE/Adverse Effects Checklist	10	
Follow up visit 1 (including alcohol consumption session)	Expired CO/Breath Alcohol	4	
	CIWA	5	
	Yale Craving Scale	5	
	Blood draw	5	
	Take dose of medication	2	
	Smoking break	15	
	TQSU	1	
	MNWS	1	

VISIT	MEASURE/PROCEDURE	TIME (MINS)
	PACS	1
	TLFB	10
	SAFTEE/Adverse Effects Checklist	8
	Cigarette Self-efficacy (SEQ)	1
	Alcohol self-efficacy (AASE)	4
	Stop signal	10
	CPT	10
	Reward Responsiveness Test	15
	Monetary Choice Questionnaire	2
	Alcohol Purchase Task	2
	Cigarette Purchase Task	2
	Food delay discounting task	4
	Weight	1
	Three Factor Eating Questionnaire	3
	Reward-Based Eating Drive Scale	2
	PROMIS Depression/BDI-II	4
	Simplified Nutritional Appetite Questionnaire	2
	Medical check-in	5
	Urine test (pregnancy, drugs, riboflavin)	5
	Priming drink + absorption	35
	TQSU	1
	BAES	1
	AUQ	1
	DEQ	1
	Ad libitum drinking session	120
	Smoking break	15
	TQSU	1
	BAES	1
	AUQ	1
	DEQ	1
	Alcohol Purchase Task	2

VISIT	MEASURE/PROCEDURE	TIME (MINS)
	Cigarette Purchase Task	2
	Smoking break	15
Washout	7 days with no medication	
	TLFB	10
	Dispense 2 nd medication	10
	Simplified Nutritional Appetite Questionnaire	2

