Between Dispensing & Follow up visit 2	Call participant on days 2 and 4 to assess side effects SAFTEE/Adverse Effects Checklist	10
Follow up visit 2 (including alcohol consumption session)	Expired CO/Breath Alcohol	4
	CIWA	5
	Yale Craving Scale	5
	Blood draw	5
	Take dose of medication	2
	Smoking break	15
	TQSU	1
	MNWS	1
	PACS	1
	TLFB	10
	SAFTEE/Adverse Effects Checklist	8
	Cigarette Self-efficacy (SEQ)	1
	Alcohol self-efficacy (AASE)	4
	Stop signal	10
	CPT	10
	Reward Responsiveness Test	15
	Monetary Choice Questionnaire	2
	Alcohol Purchase Task	2
	Cigarette Purchase Task	2
	Food delay discounting task	4
	Weight	1
	Three Factor Eating Questionnaire	3

VISIT	MEASURE/PROCEDURE	TIME (MINS)
	Reward Based Eating Drive Scale	2
	PROMIS Depression/BDI-II	4
	Simplified Nutritional Appetite Questionnaire	2
	Medical check-in	5
	Urine test (pregnancy, drugs, riboflavin)	5
	Priming drink + absorption	35
	TQSU	1
	BAES	1
	AUQ	1
	DEQ	3
	Ad libitum drinking session	120
	Smoking break	15
	TQSU	1
	BAES	1
	AUQ	1
	DEQ	1
	Alcohol Purchase Task	2
	Cigarette Purchase Task	2
	Smoking break	15

VI. *Anticipated End Date*

We anticipate completing all data collection by March of 2021. At the time of study closure, after all follow-up data have been collected, all participant identifiers (name, address, etc.) will be made inaccessible to the research team. MRN retains the link between identifiers and URSI indefinitely for the potential future benefit to the research participant. Specifically, it may become medically advantageous in the future for a former participant to have access to the clinical information that may be present in the medical screening.

VII. *Project Location(s)*

All study procedures and participant interactions will take place at the Mind Research Network.

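### The text implies that the Contemplation Ladder and Inventory of Drinking Situations are repeated on medication, but Table 1 schedules both only at baseline; followed as written, it allows no lorcaserin-placebo contrast on either scale

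*Combined protocol and SAP*

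**What the plan says.** Three places in the combined protocol and SAP bear on this point.

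- **Purpose.** Under Screening and Baseline Data Collection Visits, a set of scales is introduced with the aim "To assess potential medication effects on changes in motivation and self-efficacy for resisting alcohol/cigarettes". The set consists of alcohol and smoking items of the Contemplation Ladder, together with "alcohol and cigarette Abstinence Self-Efficacy (AASE and SEQ) and Inventory of Drinking Situations scales".
- **Rule on repetition.** The paragraph on impulsivity and learning tasks, a little further on, says that any measures already described "that would be expected to show change across sessions (or in response to medication) will be repeated at follow-up visits 1 and 2". A list of seven tasks and questionnaires follows, with neither scale among them.
- **Schedule.** In Table 1, "Contemplation Ladder" and the IDS-30 each have one row, both under the Baseline/First Dispensing Visit. The rows "Cigarette Self-efficacy (SEQ") and "Alcohol self-efficacy (AASE") appear at baseline and again at follow-up visits 1 and 2.

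The timing of treatment is explicit: "Participants will receive the first 7-day supply of pills (medication or placebo, randomized and counterbalanced) at the completion of the baseline visit". Every baseline value is therefore taken before treatment.

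**The concern.** The analysis section (II. Data Analysis/Statistical Considerations) compares lorcaserin with placebo as a within-subjects factor. For any scale, that comparison needs a value from each participant in each medication period. A scale measured only before the first pill describes the sample. It carries no information about the drug.

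The text presents the Ladder and IDS-30 as measures of medication effect, while the visit-by-visit schedule gives them only at baseline. At stake is the motivation half of the stated purpose. AASE and SEQ cover self-efficacy on treatment, but the other two scales named in the same sentence have no on-treatment row. Data not collected at the laboratory visits cannot be recovered later. Maximum likelihood, which the plan relies on for missing data, cannot help when an outcome is unobserved on treatment in every participant.

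**Working it through.** The plan gives no figure to reproduce here. The check is a count of Table 1 rows, followed by a comparison with the text and a sum of the visit minutes.

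**1. Scheduled administrations in Table 1**

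| Scale | Baseline | Follow-up 1 | Follow-up 2 |
|---|---|---|---|
| Contemplation Ladder | 1 | 0 | 0 |
| IDS-30 | 1 | 0 | 0 |
| SEQ | 1 | 1 | 1 |
| AASE | 1 | 1 | 1 |

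The washout and second dispensing rows contain neither the Ladder nor the IDS-30.

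**2. What the contrast needs**

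For participant *i*, the medication contrast is d_i = Y_i(lorcaserin) − Y_i(placebo), with one term from each follow-up visit. Under Table 1, neither term is observed for the Ladder or IDS-30. The single baseline value is common to both conditions and cancels from d_i, so it cannot stand in for either term. For SEQ and AASE, both terms are observed.

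If the repetition rule in the text is followed instead, the Ladder and IDS-30 become 1/1/1 and d_i is available for both.

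**3. Does the text settle the matter?**

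On its wording, the rule covers both scales, because the preceding paragraphs give them the purpose of detecting medication effects. The list after the rule does not name them, but that list is not exhaustive: it also leaves out AASE, SEQ and the eating scales, all of which Table 1 repeats. On the other side, no specific description of follow-up content names either scale. Both are absent from the sentence listing repeated baseline measures, the account of Follow-up Visits 1 and 2, the session questionnaires and Table 1.

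**4. Time cost of adding both scales**

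Table 1 minutes for follow-up visit 1:

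- rows before the priming drink: 129
- priming drink and absorption: 35
- four post-priming scales: 4
- ad libitum session: 120
- smoking break: 15
- four scales: 4
- two purchase tasks: 4
- smoking break: 15

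Sum: 129 + 35 + 4 + 120 + 15 + 4 + 4 + 15 = 326 minutes. Visit 2 is the same except that the post-priming DEQ is listed at 3 minutes instead of 1, giving 328.

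At their baseline durations, the Ladder and IDS-30 add 1 + 5 = 6 minutes.

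- Visit 1: 6/326 = 1.8%, new total 332 minutes
- Visit 2: 6/328 = 1.8%, new total 334 minutes

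The visits are budgeted at 6 to 8 hours (360 to 480 minutes), so both totals lie below the lower limit. Recovery time before discharge has no row in Table 1, so the remaining margin is not all free time.

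**The case against.** The strongest reply is that Table 1 does not settle what will be collected. Nothing in the documents says it overrides the text, and the repetition rule covers these scales. Table 1 also departs from the text elsewhere. The Minnesota Nicotine Withdrawal Scale is described as a repeated baseline measure but has no baseline row. Demand is to be measured after the priming drink, yet the purchase tasks have no row there. The pill count and the daily survey have no rows at all. Absence from the table is therefore weak evidence that a measure is not planned.

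This stands, and it limits the point. A reader might infer that the medication effect on motivation cannot be estimated in this trial, or that the investigators chose to measure these scales only once. The documents support neither inference. The loss follows only if Table 1 is what staff use, and the text points to an omission from the table.

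A second reply is that little depends on these scales. That also stands. The analysis section names neither scale, nor self-efficacy, among its outcomes. Aim 2 mentions motivation, so a reader might conclude that this aim loses its data. However, the analysis section lists purchase-task demand and craving as secondary outcomes and does not mention readiness to change.

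A third reply is that the documents do not give the recall period of the IDS-30, so it may not suit a 7-day medication phase. That is fair, and it is a reason to allow either remedy for each scale. It does not remove the conflict, because the text still gives the IDS-30 a medication-effect purpose.

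**Conclusion.** The point holds as a conflict between text and schedule. The text gives the Contemplation Ladder and IDS-30 the purpose of detecting medication effects and, by its general rule, implies that they are repeated on treatment. Table 1 provides 0 of the 2 on-treatment administrations that each scale would need.

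The consequence is conditional: a trial run to Table 1 would have no lorcaserin-placebo contrast on either scale, and a trial run to the repetition rule would have one. SEQ, AASE, the primary outcome, and the secondary and exploratory outcomes named in the analysis section are not affected by this point. Nor is the power calculation.

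Severity is low to moderate. The point is more than editorial because its resolution changes what is collected. The conclusion assumes that the Table 1 rows for these scales are complete as read; that part of the table appears intact.

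**What to change.** Reconcile Table 1 with the text, scale by scale.

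- **If the scale is meant to show a medication effect:** add it to Table 1 at both follow-up visits, in the block that already holds SEQ and AASE. Both visits are needed, because one alone does not give a within-person difference.
- **If the scale is not to be repeated** (for example, because the IDS-30 recall period does not suit a 7-day phase): remove it from the sentence that assigns the medication-effect purpose and describe it as a baseline measure.

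Adding both scales costs up to 6 minutes per laboratory visit, about 2% of the tabulated time, with slightly more participant burden and an edit to Table 1. Removing the purpose costs one sentence and gives up the corresponding question.
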